7.4 Summary of Overall Risks and Benefits

The majority of subjects in the ongoing 270-201 clinical study who have received 4E13 or 6E13 vg/kg doses of BMN 270 have had Grade 1 asymptomatic elevations in ALT. For most subjects, the elevations have reached only slightly above the upper limit of normal (ULN). Based on the effectiveness of transient oral corticosteroid used to suppress a presumed Class 1 (cytotoxic T-cell) response in prior studies with hepatic transduction with AAV vectors (Mingozzi, 2013), subjects were treated with 7-32 weeks of oral corticosteroids prophylactically or in response to the elevations in ALT to ensure preservation of the transduced hepatocytes. Using this approach, no sustained loss of FVIII activity has been observed in subjects with ALT elevations, consistent with maintaining a high level of hepatocyte function. Moreover, the rise in ALT levels were not accompanied by significant or lasting aberrations in other liver tests such as AST, bilirubin or albumin, indicating that extent of toxicity is limited. There has been one HIV-positive subject in the ongoing 270-302 clinical study who experienced Grade 3 asymptomatic elevations in ALT and AST, which has been attributed to an interaction between one or more of his antiretroviral therapy medications and/or unsuspected underlying hepatic disease with BMN 270. In addition, there has been one subject with Gilbert's syndrome in the ongoing 270-301 clinical study who has experienced Grade 3 asymptomatic elevations in ALT and AST. These cases have led to the exclusion of subsequent HIV-positive subjects and requirement of liver tests at Screening that are <1.25 times the upper limit of the normal range in the ongoing 270-301 and 270-302 clinical studies. Of note, two HIV-positive subjects in 270-301 and one presumed Gilbert's syndrome subject in 270-201 have received BMN 270 without experiencing any elevations in ALT to date. Overall, the literature and clinical experience with BMN 270 suggests that transient elevations in liver enzymes are expected following AAV-based gene therapy for the treatment for hemophilia A or B without any long-term concerns of hepatic injury (Manno, 2006; Nathwani, 2011; George, 2016; Miesbach, 2016; Pasi, 2016).

270-201 Amendment 8

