^b Refer to Table 9.7.8.2.1 for laboratory assessments to be included, and to Table 9.7.8.3.1 for liver tests. LTs may be monitored more or less frequently (and in particular when ALT values are >1.5x ULN) based on discussion between the Medical Monitor and the Investigator and review of subject data, but LTs will be monitored at least twice weekly during periods when a subject's ALT is ≥ 3x ULN. Patients with ALT > 1.5 ULN during the study may undergo additional evaluations (eg, imaging studies including MRI or ultrasound, additional blood tests, and/or liver biopsy) at the discretion of the investigator. Additional testing of FVIII and LTs during any study week may be performed if: (1) the ALT has increased to above ULN; (2) Increases in ALT values from prior assessment are accompanied by declines in FVIII activity level; or after a discussion between the Medical Monitor and the Investigator based on a review of subject data. If FVIII levels and/or ALT values are stable over the course of several weeks, assessment of FVIII activity and ALT levels may be adjusted based on discussion between the Medical Monitor and the Investigator.

- ^c Includes hFVIII activity level (one-stage clotting assay and chromogenic substrate assay). If a subject has used FVIII within 72 hours of a measurement day, all efforts should be made to obtain FVIII activity measurements when a 72-hour interval without FVIII use is achieved; the 72-hour wash-out period is only intended for subjects who have achieved FVIII ≥ 5 IU/dL at 16 weeks after BMN 270 infusion and who have not resumed standard of care FVIII replacement therapy. If FVIII levels are elevated or stable over the course of several weeks, assessment of FVIII activity may be adjusted based on discussion between the Medical Monitor and the Investigator. A d-dimer may be considered under circumstances in which FVIII activity levels are above the normal physiological range and/or if there is a concern for a venous thromboembolism.

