Assessment	17	18	19	20	21	22	23	24	25	26	27	28	29	30	31	32
Physical examination ^a	Х	Х	Х	Х	Х	Х	Х	Х	Х	Х	Х	Х	Х	Х	Х	Х
Weight										Х						
Assessment of Adverse Events and Concomitant Medications (including review of subject diary for bleeding and FVIII use)	Х	Х	Х	Х	Х	Х	Х	Х	Х	Х	Х	Х	Х	Х	Х	X
Vital Signs	Х	Х	Х	Х	Х	Х	Х	Х	Х	Х	Х	Х	Х	Х	Х	X
Blood chemistry, haematology, coagulation screen, and $\mathrm{CRP}^{\mathrm{b}}$				X				Х				Х				X
Urine Tests ^b				Х				Х				Х				Х
Liver Tests (local) ^b	Х	Х	X	Х	Х	Х	Х	Х	Х	X	Х	Х	X	Х	Х	Х
FVIII assays (local) ^c	Х	Х	Х	Х	Х	Х	Х	Х	Х	Х	Х	Х	Х	Х	Х	X
Liver Tests (central) ^b	Х	X	Х	Х	Х	Х	Х	Х	Х	Х	Х	Х	X	Х	Х	X
FVIII assays (central) ^d	Х	Х	Х	Х	Х	Х	Х	Х	Х	Х	Х	Х	Х	Х	Х	Х
FVIII antibody titer				Х								Х				
PCR of vector DNA in blood, saliva, urine, semen, and stools ^e				X				Х				Х				X
Exploratory biomarker assessments ^f				Х				Х				Х				X
Haemo-QoL-A QoL assessment												Х				
AAV5 antibody titer				Х				Х				Х				X
PBMC collection	Х	Х	Х	Х		Х		Х		Х		Х		Х		Х
Von Willebrand Factor Antigen (VWF:Ag)				Х				Х				Х				Х
Direct Thrombin test										X						

Table 9.1.3: Schedule of Events – Safety Follow-Up (Week 17-32)

* Visit windows are \pm 48 hours

^a Brief physical examination should be done at all weekly visits. Refer to Section 9.7.8.5.

Proprietary and Confidential

270-201 Amendment 8

^b Refer to Table 9.7.8.2.1 for laboratory assessments to be included, and to Table 9.7.8.3.1 for liver tests. LTs may be monitored more or less frequently (and in particular when ALT values are >1.5x ULN) based on discussion between the Medical Monitor and the Investigator and review of subject data, but LTs will be monitored at least twice weekly during periods when a subject's ALT is \geq 3x ULN. Patients with ALT > 1.5 ULN during the study may undergo additional evaluations (eg, imaging studies including MRI or ultrasound, additional blood tests, and/or liver biopsy) at the discretion of the investigator. Additional testing of FVIII and LTs during any study week may be performed if: (1) the ALT has increased to above ULN; (2) Increases in ALT values from prior assessment are accompanied by declines in FVIII activity level; or after a discussion between the Medical Monitor and the Investigator based on a review of subject data. If FVIII levels and/or ALT values are stable over the course of several weeks, assessment of FVIII activity and ALT levels may be adjusted based on discussion between the Medical Monitor and the Investigator.

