^f Blood samples will be collected to evaluate biochemical, molecular, cellular, and genetic/genomic aspects relevant to hemophilia A, coagulation, and/or AAV gene transfer, and to develop assays used for these evaluations. Subjects may choose to opt out of the exploratory genetic/genomic research being done to study or try to discover genes that are not yet known to be associated with hemophilia A. While exploratory samples will be collected at the time points indicated above, testing of these samples (including those for Direct Thrombin Activity test and any other exploratory assessments) will be performed only as deemed necessary by the Sponsor.

270-201 Amendment 8

					1	Year 1 –	Weeks	*				
Assessment	33	34	35	36	38	40	42	44	46	48	50	52
Physical examination ^a	Х	Х	Х	Х	Х	Х	Х	Х	Х	Х	Х	X
Weight ^a												X
Assessment of Adverse Events and Concomitant Medications (including review of subject diary for bleeding and FVIII use)	Х	X	Х	Х	Х	Х	Х	Х	Х	X	X	X
Vital Signs	Х	Х	Х	Х	Х	Х	Х	Х	Х	Х	Х	X
Blood chemistry, haematology, coagulation screen, and CRP ^b				Х		Х		Х		Х		Х
Urine Tests ^b				Х		Х		Х		Х		Х
Liver Tests (local) ^b	Х	Х	Х	Х	Х	Х	Х	Х	Х	Х	X	Х
FVIII assays (local) ^c	Х	Х	Х	Х	Х	Х	Х	Х	Х	Х	Х	Х
Liver Tests (central) ^b	Х	Х	Х	Х	Х	Х	Х	Х	Х	X	X	X
FVIII assays (central) ^d	Х	Х	Х	Х	Х	Х	Х	Х	Х	X	X	X
AAV5 antibody titer				Х		Х		Х		X		X
FVIII antibody titer				Х				Х				Х
PBMC Collection (for determination of FVIII and Capsid specific CTL activity)		X		Х				Х				X
Von Willebrand Factor Antigen (VWF:Ag)				Х		Х		Х		X		X
Direct Thrombin Test					Х							Х
PCR of vector DNA in blood, saliva, urine, semen, and stools ^e				Х		Х		Х		Х		Х
Exploratory biomarker assessments ^f				Х		Х		Х		Х		Х
Haemo-QoL-A QoL assessment												X

Table 9.1.4: Schedule of Events – Safety Follow-Up (Week 33-52)

* Visit windows are \pm 48 hours through Week 36, then \pm 1 week until Week 52.

^a Complete physical examination should be performed at Week 52; brief physical examination may be performed at other study visits. Refer to Section 9.7.8.5.

^b Refer to Table 9.7.8.2.1 for laboratory assessments to be included, and to Table 9.7.8.3.1 for liver tests. LTs may be monitored more or less frequently (and in particular when ALT values are >1.5x ULN) based on discussion between the Medical Monitor and the Investigator and review of subject data, but LTs will be monitored at least twice weekly during periods when a

Proprietary and Confidential

31 January 2019

270-201 Amendment 8

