^b Following initiation or completion of steroid regimen, if ALT elevation ≥ 1.5x ULN is reported, steroid management decisions will based on discussions between the Investigator and Medical Monitor. Modification of the steroid regimen may take into consideration possible confounders for the ALT elevation and impact on FVIII expression.

^c After discontinuation of corticosteroids, weekly labs for ALT and FVIII levels will be measured once a week for 4 weeks to ensure stability in values. If these assessments are already being done as part of normal study follow-up, they do not need to be duplicated.

^d Regardless of the assessments listed in the Schedule of Assessments (Table 9.1.2, Table 9.1.3, or Table 9.1.4), subjects initiated on corticosteroids will only be required to have laboratory evaluations on a weekly basis.

^e Should only be performed in subjects with a history of hepatitis B or hepatitis C prior to study entry.

270-201 Amendment 8

	Within 28 Days Before Biopsy Day	Within 7 Days Before Biopsy Day	1 Day Before Biopsy Day ^d	Biopsy Day (BD)
Informed Consent	Х			
Liver Ultrasound ^a	X			
Brief Physical Examination	X		X	Х
Hematology, Coagulation, Chemistry Assessments ^b	X		X	
Liver Tests ^b	X		X	Х
FibroScan		Х		
Local FVIII Activity Level Assessment		Х	X	Х
Pre-Biopsy Consultation ^c		Х		
Liver Biopsy ^e				Х

Table 9.1.7: Schedule of Events – Liver Biopsy Substudy

^a Liver ultrasound must be performed within 28 days prior to the scheduled biopsy, unless an ultrasound result from the prior 3 months is already available.

^b Refer to Table 9.7.8.2.1 for laboratory assessments to be included, and to Table 9.7.8.3.1 for liver tests.

^c Subjects will undergo a pre-biopsy consultation with the investigator (treating hematologist).

^d Subjects may need to repeat/extend this visit if their FVIII activity levels need adjustment before the biopsy, at the discretion of the investigator (treating hematologist).

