9.4.8.2.1 Therapeutic Corticosteroids

In general, therapeutic corticosteroids may be initiated when a subject's ALT value is $\geq 1.5x$ ULN, or based on review of FVIII and liver enzyme data after consultation between the Medical Monitor and the Investigator.

Reports of raised LTs (defined as $ALT \ge 1.5x$ ULN) should be made to the BioMarin medical monitor within 30 minutes of the lab value being available. Local laboratory results of LTs will be used to trigger corticosteroid treatment as needed. In case of discrepant results between local and central laboratories, the Investigator and Medical Monitor will decide further action.

Following initiation or completion of therapeutic corticosteroids, if ALT elevation $\geq 1.5x$ ULN is reported, steroid management decisions will based on discussions between the Investigator and Medical Monitor. Modification of the steroid regimen may take into consideration possible confounders for the ALT elevation and impact on FVIII expression.

270-201 Amendment 8

Treatment with prednisolone will be initiated at a dose of 60 mg per day and then gradually tapered (60 mg daily for the first 2 weeks, then 40 mg the next 2 weeks, then 30 mg the next two weeks, then 20 mg the next two weeks, then 15 mg for the next week, then 10 mg for the next week, then 5 mg for the next week, then stop, for a total treatment of 11 weeks) (refer to Table 9.1.6).

After discontinuation of corticosteroids, weekly labs for ALT and FVIII levels will be measured once a week for 4 weeks to ensure stability in values.

Management and monitoring of reactions to corticosteroids should be determined by the Investigator's clinical judgment in consultation with the Sponsor's Medical Monitor. This includes the contraindicated use of NSAIDs during corticosteroid treatment, and specific monitoring not already covered by the schedule of events. For the subjects with a past medical history of hepatitis B or hepatitis C prior to study entry, Hepatitis B status and HCV viral load will be rechecked 6 weeks after the start of corticosteroid treatment, and then 1 week and 13 weeks after the completion of corticosteroid treatment. All adverse events should be reported as outlined in Section 10 of the protocol.

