Subjects who undergo smart rescreening must complete the rescreening assessments and receive the infusion within 90 days of signing the original consent. Subjects who do not complete dosing within 90 days will be required to re-consent and undergo all screening procedures. Subjects may not undergo smart rescreening more than once.

If a patient has to be screened again because the original assessments have fallen out of the 28 + 14 day period allowed for Screening (refer to Section 12.2), then only the following assessments need to be performed (rather than the full list indicated in Section 12.2) for the patient to be successfully re-screened for the study:

- Vital signs
- Assessment of Adverse Events and Concomitant Medications
- Documentation of bleeding episodes and FVIII usage (by either subject or clinical information)
- hFVIII Assays (only the hFVIII inhibitor level (Bethesda assay with Nijmegen modification)

- Blood sample for AAV5 Assays
 - o AAV5 antibody titer
 - o AAV5 transduction inhibition assay
- Blood chemistry, haematology, coagulation screen, and CRP (refer to Table 9.7.8.2.1)
- Urine Tests (refer to Table 9.7.8.2.1)
- Liver Tests (refer to Table 9.7.8.3.1)

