Rationale: The original timing (which required visits on every 4 week, every 6 week, and every 3 month schedules) created burdens on sites in trying to align visits within allowed visit windows to minimize subject burden. The revised timing (which has substituted visits every 12 weeks and at specified end of year timepoints for the every 3 month visits) has simplified the calendar of visits and should ease site burden.

3. An abbreviated visit schedule has been made available during Years 2-5 for subjects who are considered to have not responded to BMN 270 therapy.

Rationale: Treatment failure—manifesting as either failure to achieve FVIII activity ≥ 5 IU/dL by Week 52 or inability to maintain independence from prophylactic FVIII replacement therapy due to joint bleeding episodes, in the judgment of the Investigator may, at the Investigator's discretion and after discussion with the Medical Monitor, enable subjects to follow an abbreviated visit schedule after Week 52 of the study by attending only the Q12W and End of Year visits during Years 2-5.

Subjects who meet the "treatment failure" definition and wish to follow an abbreviated schedule but who have not cleared vector shedding from all fluids must still provide samples for assessment every 4 weeks (during Year 2) or every 6 weeks (during Years 3-5) until

Proprietary and Confidential

vector shedding has cleared (but do not need to perform other assessments at those study visits).

4. Additional details have been included concerning information to be collected as part of the medical history.

Rationale: In subjects with a history of hepatitis B or hepatitis C infection, information on the specific treatments received for that infection should be collected. In addition, any previous pharmacokinetic data collected at the time the subject was receiving on-demand or prophylactic FVIII treatment should be collected. This additional history data could help explain a subject's FVIII response (or lack of FVIII response) to BMN 270. As all subjects have already gone through Screening and reported medical history during 270-201, this additional history should be collected at the next regularly scheduled study visit (or at least prior to the end of the subject's participation in the study).

5. Language concerning when to consider restarting FVIII prophylaxis following BMN 270 infusion has been modified.

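### Table 9.1.6 footnote d sets weekly labs for subjects on corticosteroids without excepting the twice-weekly liver-test floor at ALT ≥3x ULN

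*Protocol*

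**What the plan says.** Two rules in Section 9.1 of the protocol (Amendment 8) govern how often liver tests are done.

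- **Footnote b of Tables 9.1.2 (Weeks 1-16), 9.1.3 (Weeks 17-32) and 9.1.4 (Weeks 33-52).** The frequency may go up or down after discussion between the Medical Monitor and the Investigator, but with a lower limit: "LTs will be monitored at least twice weekly during periods when a subject's ALT is" at or above 3x ULN.
- **Table 9.1.6 footnote d, attached to the steroid treatment period.** It opens by setting aside the assessments listed in Tables 9.1.2, 9.1.3 or 9.1.4 and then states that "subjects initiated on corticosteroids will only be required to have laboratory evaluations on a weekly basis". It gives no ALT-dependent exception.

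On when steroids begin, Section 9.4.8.2.1 says that "therapeutic corticosteroids may be initiated when a subject's ALT value is" at or above 1.5x ULN, or after review of FVIII and liver enzyme data.

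**The concern.** The floor is worded as an obligation, and footnote d as an override of the tables that contain it. A subject whose ALT has reached 3x ULN has already passed the steroid trigger, so he may well be on the regimen that footnote d governs. If footnote d prevails, the more frequent hepatic check is no longer required for a subject on steroids.

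A site could then do one liver test a week and point to footnote d as compliance, while a monitor could cite footnote b and record the same conduct as a deviation. In a first-in-human gene therapy study, a required liver-safety frequency should not depend on which footnote the site reads.

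**Working it through.** No sample size, power or estimate is involved, so the check is a comparison of the texts.

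**1. The two rules side by side**

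| | Footnote b, Tables 9.1.2-9.1.4 | Footnote d, Table 9.1.6 |
|---|---|---|
| Who | Any subject with ALT ≥3x ULN | Any subject started on corticosteroids |
| When | Year 1 (Weeks 1-52) | Steroid treatment period, setting aside Tables 9.1.2-9.1.4 |
| What | Liver tests | Laboratory evaluations |
| Required minimum | At least 2 per week | 1 per week |
| Exception stated | None for subjects on steroids | None for ALT ≥3x ULN |

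**2. Do the two groups overlap?** The steroid trigger is ALT ≥1.5x ULN (Section 9.4.8.2.1; Table 9.1.6 footnote a) and the floor starts at ALT ≥3x ULN. Since 1.5 < 3, every subject at the floor has also met the steroid trigger. Starting steroids is permitted, not obligatory, so the overlap is likely but not automatic.

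**3. Does the grid of Table 9.1.6 settle it?** No. It marks liver testing in post-steroid Weeks 1-4 and none in steroid Weeks 1-11. Footnote d is therefore the only liver-test frequency that table gives for the treatment period.

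**4. Does other text settle it?** Section 9.4.8.2 and Sections 12.5.1, 12.6.1 and 12.7.1 leave the frequency to discussion. Section 9.4.8.2.1 gives the taper and refers to Table 9.1.6. None of them says which footnote prevails. That they do not repeat the floor is ordinary non-duplication and no fault in itself.

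**5. Size per affected week.** Required minimum under footnote d: 1. Under footnote b: at least 2. Shortfall: at least 2 − 1 = 1 test, so the required minimum is halved.

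**6. Enrollment-halt criterion.** Section 9.3.4.1 halts enrollment on ALT above 5x ULN for at least 2 consecutive weeks. One test a week can still show that pattern, so the criterion works under either footnote.

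**The case against.** The strongest reply is that footnote d was never meant to touch the floor. It fills a blank in the Table 9.1.6 grid with a routine cadence. After Week 1 the scheduled grids never ask for liver tests more than weekly, and from Week 38 they ask every two weeks, so for scheduled liver tests footnote d matches or raises the frequency. It may also mean labs only, sparing subjects the other visit procedures. Footnote b is narrower (one type of test, one ALT condition), and a specific rule is often taken to stand on top of a general one. The amendment history, useful for intent only, points the same way: footnote d has the same words in Amendment 6, when the tables had no floor, and the Amendment 7 summary of changes (item 12) introduces the floor as a mandate.

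Much of this stands. It makes an oversight more likely than a deliberate exemption, and it is why confidence is medium. It does not remove the point, because footnote d names the tables that hold the floor, sets them aside and states no exception.

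A reader might infer three stronger things that the documents do not support:

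- **That footnote d forbids more frequent testing.** It fixes only what is required. Extra tests remain available under footnote b.
- **That sustained severe elevations would go unseen.** ALT ≥1.5x ULN must be reported to the medical monitor within 30 minutes (Section 9.4.8.2.1) and as an event of special interest within 24 hours (Section 10.2.1). The halt criterion is unaffected.
- **That the shortfall can be multiplied over a whole steroid course.** Section 7.4 says that "subjects were treated with 7-32 weeks of oral corticosteroids", but this includes prophylactic use and does not measure time at ALT ≥3x ULN. The protocol gives no such duration.

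**Conclusion.** The point holds as a minor wording conflict, with medium confidence. Read literally, the guaranteed Year 1 floor is lost for subjects on steroids: one required liver test instead of at least two in each week with ALT at or above 3x ULN. Read as a cadence with the floor on top, nothing is lost, but the protocol does not state that reading.

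Few subjects are likely to be affected, possibly none. Section 7.4 describes mostly Grade 1 ALT elevations in this study, for most subjects only slightly above ULN, and the Grade 3 cases it names come from studies 270-301 and 270-302. By Amendment 7 enrollment was past screening: "As all subjects have already gone through Screening and reported medical history during 270-201". The last dosing date is not given, so it cannot be said that Year 1 was over for everyone under Amendment 8. No endpoint, estimate or halt criterion changes.

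**What to change.** Add one clause to the end of Table 9.1.6 footnote d: *except that, while ALT is at or above 3x ULN, liver tests are done at least twice a week.* This states the cadence-plus-floor reading outright and leaves the weekly rule intact for all other laboratory work.

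It can go into a clarification letter or the next amendment. The cost is a few extra blood draws in any subject who reaches ALT 3x ULN while on corticosteroids.
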